2.3 Exploratory Objectives & Endpoints

2.3.1 To assess the predictive value of baseline iSCORE and PDL-1 expression using archival tissue samples as well as any standard of care tissue obtained during study treatment.

All patients will provide archival or fresh tumor tissue at study registration, and will have the option to provide tissue from any biopsies performed during study treatment.

3.0 PATIENT ELIGIBILITY

The target population for this study is patients with stage IV early recurrence HER2 negative IBC. This will be a single center trial conducted at Northwestern University.

A total of 29 subjects will be needed for this trial. Approximately 8 potentially eligible patients are seen per month, and it is anticipated that at least 2 per month will be accrued. Potential patients may be referred to the Principal Investigator (PI) at Northwestern University, [name] at [contact].

Eligibility will be evaluated by the study team according to the following criteria. Eligibility waivers are not permitted. Subjects must meet all of the inclusion and none of the exclusion criteria to be registered to the study. Study treatment may not begin until a subject is registered. Please refer to Section 11.3 for complete instructions regarding registration procedures.

3.1 Inclusion Criteria

3.1.1 Patients must have histologically or cytologically confirmed stage IV breast carcinoma with a previous clinical diagnosis of IBC based on the presence of inflammatory changes in the involved breast, such as diffuse erythema and edema (peau d'orange), with or without an underlying palpable mass involving the majority of the skin of the breast. Pathological evidence of dermal lymphatic invasion should be noted but is not required for diagnosis.

3.1.2 Patients must have local or metastatic recurrence of IBC after prior surgery.

3.1.3 Patients must have a metastatic tumor negative for HER2. The lack of HER2 overexpression by immunohistochemistry (IHC), is defined as 0 or 1+ where as hyperexpression is defined as 3+. If equivocal IHC, 2+, the tumor must be non-gene amplified by FISH performed upon the primary tumor or metastatic lesion (ratio <2 and HER2 copy number <4).⁴⁷

3.1.4 Patients may have measurable disease, defined as at least one lesion that can be accurately measured in at least one dimension in accordance with RECIST criteria v. 1.1 OR non-measurable tumors (see section 6.5).

NOTE: Non-measurable tumors are small lesions (longest diameter <10mm or pathological lymph nodes with ≥ 10 to <15 mm short axis). Bone lesions, ascites, pleural/pericardial effusions, lymphangitis cutis/pulmonitis, inflammatory breast disease, and abdominal masses (not followed by CT or MRI) are considered as non-measurable.

3.1.5 Patients must be in consideration for 1st line systemic therapy for recurrent IBC.

NOTE: Patients must not have received chemotherapy in the metastatic setting, but adjuvant treatment after surgery is acceptable.

3.1.6 Patients must have confirmed availability of archival or freshly biopsied tumor tissue meeting protocol-defined specifications prior to study enrollment.

3.1.7 Patients must be female and age ≥ 18 years.

3.1.8 Patients must exhibit an ECOG status of 0-1. ECOG performance status 2 and 3 will be allowed only if decline in performance status is thought to be directly secondary to breast cancer disease burden by treating physician.

3.1.9 Patients must have adequate organ and bone marrow function ≤ 14 days prior to registration, as defined below:

• leukocytes	$\geq 2,000/\text{mCL}$
• absolute neutrophil count	$\geq 1,500/\text{mCL}$, regardless of transfusion or growth factor support
• platelets	$\geq 100,000/\text{mCL}$, regardless of transfusion or growth factor support
• total bilirubin	total bilirubin $\leq 1.5 \times$ institutional upper limit of normal (ULN) (except patients with Gilbert Syndrome or liver metastasis, who can have total bilirubin $< 3.0 \times$ ULN)
• AST(SGOT)/ALT(SPGT)	$\leq 2.5 \times$ institutional upper limit of normal (ULN) (or ≤ 5 times ULN in case of liver metastasis)
• creatinine	Serum creatinine of $< 3.0 \times$ ULN (upper limit of normal)

NU Study Number: NU 16B07
Other Study Number: CA 209-782

3.1.10 Patients with history of central nervous system (CNS) metastases are eligible if CNS disease has been stable for at least 6 weeks prior to study registration in the opinion of the investigator and do not require corticosteroids (of any dose) for symptomatic management.

NOTE: Patients are not required to have CNS imaging prior to study entry.

3.1.11 Females of childbearing potential (FOCBP) must have a negative serum or urine pregnancy test (minimum sensitivity 25 IU/L or equivalent units of HCG) within 72 hours of registration.

NOTE: A FOCBP is *any woman* (regardless of sexual orientation, having undergone a tubal ligation, or remaining celibate by choice) who meets the following criteria:

- *Has not* undergone a hysterectomy or bilateral oophorectomy
- *Has had* menses at any time in the preceding 12 consecutive months (and therefore has not been naturally postmenopausal for > 12 months)

3.1.12 FOCBP and men who are sexually active with FOCBP must agree to follow instructions for method(s) of contraception for the duration of treatment and the designated post-treatment period (see Appendix C for details on appropriate contraception methods)

3.1.13 Patients must have the ability to understand and the willingness to sign a written informed consent prior to registration on study.

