If PD is confirmed at any time, see section 4.4 on how to determine whether patient can be considered for further treatment. If patient continues, scans should be obtained every 12 weeks until PD is confirmed by 2 consecutive scans.

⁴ CBC with differential will include WBC, ANC, ALC, Platelets, and Hemoglobin. It will be collected within 14 days of registration, every 14 days during cycles 1 & 2, and prior to each treatment thereafter (day 1, 29, 43, and 57 of each cycle).

⁵ Chemistry panel will include glucose, calcium, albumin, ALT, AST, sodium, potassium, total bilirubin, alk phos, and creatinine. It will be collected within 14 days of registration, every 14 days during cycles 1 & 2, and prior to each treatment thereafter (day 1, 29, 43, and 57 of each cycle).

⁶ Amylase and lipase will be assessed at screening and Day 1 of each cycle.

⁷ TSH will be tested at screening and Day 1 of each cycle. If TSH is abnormal, free T4 should be tested

⁸ Serum or urine test for females of child-bearing potential (FOCBP) within 72 hours of registration. FOCBP are also required to have a negative pregnancy test within 24 hours of starting nivolumab and Day 1 of each cycle.

⁹ Nivolumab will be administered IV at 240mg over 30 minutes every two weeks in combination with ipilimumab as follows:
Cycle 1, C2D1, & C2D15: 240mg over 30 minutes (-5 / +15 minutes) every 14 days.

Starting with Cycle 2 Day 29: 480mg over 60 minutes (-10 / +15 minutes) every 28 days until PD, intolerance, or withdrawal of consent.

¹⁰ Ipilimumab will be administered IV at 1mg/kg over 90 minutes every six weeks in combination with nivolumab. Dosing will be based on body weight measured every 6 weeks, prior to each ipilimumab infusion. Nivolumab will be given before ipilimumab.

¹¹ Archival tissue (or fresh tissue if not available) will be collected at baseline for all patients. If the patient agrees, additional tissue may be collected during biopsies performed as standard of care during study participation. Please see separate lab manual for details.

¹² Treatment will start within 14 days of registration, and continue until confirmed disease progression, unacceptable toxicity, or withdrawal of consent.

¹³ Study procedures may take place within 24 hours prior to study treatment.

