Appendix C – Contraception Requirements

Investigators shall counsel FOCBP and male subjects who are sexually active with FOCBP on the importance of pregnancy prevention and the implications of an unexpected pregnancy. Investigators shall advise FOCBP and male subjects who are sexually active with FOCBP on the use of highly effective methods of contraception. Highly effective methods of contraception have a failure rate of < 1% per year when used consistently and correctly.

At a minimum, subjects must agree to the use of two methods of contraception, with one method being highly effective and the other method being either highly effective or less effective as listed below:

HIGHLY EFFECTIVE METHODS OF CONTRACEPTION

- a) Male condoms with spermicide
- b) Hormonal methods of contraception including combined oral contraceptive pills, vaginal ring, injectables, implants, and intrauterine devices (IUDs) such as Mirena® by FOCBP subject or male subject's FOCBP partner. Female partners of male subjects participating in the study may use hormone based contraceptives as one of the acceptable methods of contraception since they will not be receiving study drug.
- c) Nonhormonal IUDs, such as ParaGard®
- d) Tubal ligation
- e) Vasectomy.
- f) Complete Abstinence*

*Complete abstinence is defined as complete avoidance of heterosexual intercourse and is an acceptable form of contraception for all study drugs. Subjects who choose complete abstinence are not required to use a second method of contraception, but female subjects must continue to have pregnancy tests. Acceptable alternate methods of highly effective contraception must be discussed in the event that the subject chooses to forego complete abstinence.

LESS EFFECTIVE METHODS OF CONTRACEPTION

- a) Diaphragm with spermicide
- b) Cervical cap with spermicide
- c) Vaginal sponge
- d) Male Condom without spermicide*
- e) Progestin only pills by FOCBP subject or male subject's FOCBP partner
- f) Female Condom*

[figure not shown]
*A male and female condom must not be used together

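### The menses test in 3.1.11, read literally, exempts women with treatment-induced amenorrhea of 12 months or more from pregnancy testing and contraception, although its own gloss points to natural menopause only

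*Combined protocol and SAP*

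**What the plan says.** Section 3.1.11 requires a negative pregnancy test around registration for every FOCBP. It defines the term by two criteria that must both be met. The first is anatomical: no hysterectomy and no bilateral oophorectomy. The second is that she has had "menses at any time in the preceding 12 consecutive months (and therefore has not been naturally postmenopausal for > 12 months". The same note keeps a woman in the FOCBP group even after tubal ligation or if she is celibate.

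Other requirements use the term without redefining it:

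- Section 3.1.12: "FOCBP and men who are sexually active with FOCBP must agree to follow instructions for method(s) of contraception".
- Section 5.0, footnote 8: "Serum or urine test for females of child-bearing potential (FOCBP) within 72 hours of registration", and then "FOCBP are also required to have a negative pregnancy test within 24 hours of starting nivolumab and Day 1 of each cycle".
- Appendix C: "At a minimum, subjects must agree to the use of two methods of contraception, with one method being highly effective". Complete abstinence is the alternative: "Subjects who choose complete abstinence are not required to use a second method of contraception, but female subjects must continue to have pregnancy tests".

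Section 3.0 adds "Eligibility waivers are not permitted". No section mentions amenorrhea caused by chemotherapy, endocrine therapy or ovarian suppression.

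**The concern.** The two halves of one bullet classify the same woman differently. The operative half asks only whether she has menstruated in the past year. The parenthesis describes the woman to be exempted as naturally postmenopausal, but it is worded as a consequence of the menses test, not as a condition of its own.

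A site that applies the operative half could enrol a woman with intact uterus and ovaries and long treatment-induced amenorrhea without any pregnancy test, and treat her without a contraception agreement. If her ovarian function can recover, a pregnancy could be missed at entry. It could also begin on nivolumab and ipilimumab before a return of menses brings her under the FOCBP rules. This is a participant-safety matter only.

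**Working it through.** The plan gives no figure on this point, so there is none to reproduce. The check is one of logic, followed by a count of the tests at issue.

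**1. Classification.** Literal rule: FOCBP = (no hysterectomy or bilateral oophorectomy) AND (menses in the past 12 months). Rule implied by the gloss: FOCBP = (no hysterectomy or bilateral oophorectomy) AND NOT (naturally postmenopausal for more than 12 months). For women with uterus and ovaries intact:

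| Woman | Literal rule | Rule implied by gloss |
|---|---|---|
| Menses within 12 months | FOCBP | FOCBP |
| Treatment-induced amenorrhea, under 12 months | FOCBP | FOCBP |
| Natural menopause, over 12 months | not FOCBP | not FOCBP |
| Treatment-induced amenorrhea, 12 months or more | **not FOCBP** | **FOCBP** |

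The inference in the bullet is valid in one direction: recent menses imply that she is not naturally postmenopausal. The converse fails, because absent menses do not imply natural menopause. The last row is the gap.

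**2. Whether the trial can enrol her.** Patients are women aged 18 or older (3.1.7) with recurrence after surgery (3.1.2), and adjuvant treatment is accepted (3.1.5). Section 1.1 describes standard care as anthracycline and taxane chemotherapy before surgery, with adjuvant endocrine therapy where indicated. Section 4.5.1 permits antihormonal therapy on study. Started on study, that cannot produce 12 months of amenorrhea before registration, so it matters only for women who began it well beforehand.

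**3. What else would catch her.** Section 3.2.9 excludes pregnant patients, section 11.3 has the quality assurance monitor confirm eligibility, and section 4.8 lists pregnancy as a reason for removal. None of these requires a test.

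**4. Tests per woman** (footnotes 8 and 12 and the 5.0 schedule; one cycle is 12 weeks).

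- Registration and first dose: 1 test if one sample meets both windows, otherwise 2. They can fall apart because "Treatment will start within 14 days of registration".
- Cycle 2 Day 1 (week 13): 1. Cycle 3 Day 1 (week 25): 1.
- Off treatment: 0 or 1, because it is marked in the schedule row but not mentioned in footnote 8.

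FOCBP reaching Cycle 3 Day 1: minimum 1 + 1 + 1 + 0 = 3; maximum 2 + 1 + 1 + 1 = 5.
FOCBP stopping before week 13: minimum 1 + 0 = 1; maximum 2 + 1 = 3.

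The literally exempt woman has 0 tests at registration and first dose. If she is followed to Cycle 3 Day 1:

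- menses return in Cycle 1: 1 + 1 = 2, plus 0 or 1, so 2 to 3;
- menses return in Cycle 2: 1, plus 0 or 1, so 1 to 2;
- menses do not return: 0.

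**5. Number of women.** The documents give no ages, menopausal status or amenorrhea rates. On purely assumed fractions of 0% to 20% of the 29 patients, the exempt group is 0 to 29 × 0.20 = 5.8 women. If amenorrhea is reversible in 0% to 50% of them, 0 to 5.8 × 0.50 = 2.9 could still be fertile. This is assumed fractions multiplied by 29. It shows scale and is not an estimate.

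**The case against.** The strongest reply is that the sentence already gives the answer. The word for natural menopause is on the page, and a careful investigator would read the exemption as limited to it. That is fair as to intent, and it makes this a wording repair rather than a flawed policy. It does not settle practice, because a site or monitor checking the criterion as written would check for menses.

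A second reply is that the harm rests on facts outside the documents: that prior treatment can cause amenorrhea lasting a year, and that this is sometimes reversible. This stands. If it is never reversible, there is no harm. The conflict within the bullet does not depend on it.

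A third is that the group is narrow. It needs at least 12 months without menses before registration, in a population that section 3.0 describes as early recurrence. Section 1.1 puts estrogen receptor expression in IBC at 30 to 44%, so the endocrine route probably concerns a minority. The chemotherapy route remains.

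A fourth is that other safeguards exist. Medical history, physical examinations and pelvic imaging are scheduled (5.0), the investigator may exclude for safety (3.2.7), and any reported pregnancy must be followed (7.3). These give context, but none replaces a required pregnancy test.

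**Conclusion.** The point holds as a safety clarification worth making. The literal menses test and its gloss disagree about one group of women, and for that group every required pregnancy test and the contraception agreement depend on which half is followed. The difference is 3 to 5 tests against none for a woman who reaches Cycle 3 Day 1 without return of menses. The number of women is unknown and may be zero, and the harm assumes some reversibility.

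Three stronger readings are tempting and unsupported. A reader might infer that the protocol deliberately leaves potentially fertile women untested; the gloss points the other way. A reader might take 2.9 women as the expected number at risk; it is the top of an assumed range. A reader might infer that the trial's results are at risk; no endpoint, estimate or decision rule is affected.

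**What to change.** Reword the second criterion of 3.1.11 so that natural menopause is the condition itself, for example: *Is not naturally postmenopausal, meaning more than 12 months without menses and with no other cause. Amenorrhea that began during or after chemotherapy, ovarian suppression or other drug therapy does not by itself count as natural menopause.* Section 3.1.12, footnote 8 and Appendix C then follow through the defined term.

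An open-ended exception for women judged postmenopausal by age or hormone levels should not be added. Without thresholds it could exempt the same women again, since a hormone level taken during ovarian suppression may look postmenopausal (general knowledge, not in the documents). If an exception is wanted, state a fixed age cut-off and bar hormone levels taken during suppression.

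The cost is a short amendment and about 1 to 5 urine or serum tests per reclassified woman up to Cycle 3 Day 1, at visits already scheduled, then one per further 12-week cycle. The larger downside is that two contraceptive methods or complete abstinence become an eligibility condition for a few women who may be infertile. With no waivers allowed, one who declines cannot enrol. A fixed age cut-off would spare the clear cases.

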3.2 Exclusion Criteria

3.2.1 Patients must not have had chemotherapy or radiotherapy \leq 28 days prior to study registration.

3.2.2 Patients who already received chemotherapy for recurrent metastatic IBC are not eligible.

3.2.3 Patients who have not recovered to \leq Grade 1 from adverse events due to agents administered \geq 28 days prior to registration are not eligible.

3.2.4 Patients may not be receiving any other investigational agents.

3.2.5 Patients who have had prior exposure to immune checkpoint inhibitors are not eligible. Please contact principal investigator, [name] at [contact] for specific questions on potential interactions.

Mechanism of action	Agent
PD-1 monoclonal antibody	Pembrolizumab, Pidilizumab, MEDI-0680, AMP-224, PF-06801591, AMP224, BGB-A317, PDR001, REGN2810, SHR-1210
PD-L1 monoclonal antibody	Durvalumab, avelumab, MDX-1105, atezolizumab, MPDL3280A
CTLA4 monoclonal antibody	Tremelimumab, abatacept
OX40	MEDI6383, MEDI6469, MEDI0562, oxatumab, PF-04518600

NU Study Number: NU 16B07
Other Study Number: CA 209-782

3.2.6 Patients with active autoimmune disease or history of autoimmune disease that might recur, which may affect vital organ function or require immune suppressive treatment including chronic prolonged systemic corticosteroids (defined as corticosteroid use of duration one month or greater), should be excluded. These include but are not limited to patients with a history of:

- immune related neurologic disease
- multiple sclerosis
- autoimmune (demyelinating) neuropathy
- Guillain-Barre syndrome
- myasthenia gravis
- systemic autoimmune disease such as SLE
- connective tissue diseases
- scleroderma
- inflammatory bowel disease (IBD)
- Crohn's
- ulcerative colitis
- patients with a history of toxic epidermal necrolysis (TEN)
- Stevens-Johnson syndrome
- anti-phospholipid syndrome
- leptomeningeal disease

NOTE: Subjects with vitiligo, type I diabetes mellitus, residual hypothyroidism due to autoimmune condition only requiring hormone replacement, psoriasis not requiring systemic treatment, or conditions not expected to recur in the absence of an external trigger are permitted to enroll.

3.2.7 Patients who have an uncontrolled intercurrent illness including, but not limited to any of the following, are not eligible:

- Ongoing or active infection (including minor localized infections) requiring oral or IV treatment
- Symptomatic congestive heart failure, defined as a clinical syndrome resulting from any structural or functional cardiac disorder that impairs the ability of the ventricle to fill with or eject blood
- Unstable angina pectoris
- Cardiac arrhythmia
- Psychiatric illness/social situations that would limit compliance with study requirements
- Any other illness or condition that the treating investigator feels would interfere with study compliance or would compromise the patient's safety or study endpoints

3.2.8 Patients should not have any condition requiring systemic treatment with corticosteroids (<10mg daily prednisone equivalents) or other immunosuppressive medications ≤14 days prior to registration.

NOTE: Inhaled or topical steroids and adrenal replacement steroid doses <10mg daily prednisone equivalents are permitted in the absence of active autoimmune disease. A brief (less than 3 weeks) course of corticosteroids for prophylaxis (eg, contrast dye allergy) or for treatment of non-autoimmune conditions (eg, delayed-type hypersensitivity reaction caused by a contact allergen) is permitted.

3.2.9 Female patients who are pregnant or nursing are not eligible.

NU Study Number: NU 16B07
Other Study Number: CA 209-782

3.2.10. Patients with a history of another malignancy within 3 years prior to registration are not eligible for participation, with the following exceptions:

- adequately treated basal cell or squamous cell skin cancer,
- in situ cervical cancer

3.2.11 Known history of testing positive for human immunodeficiency virus (HIV) or known acquired immunodeficiency syndrome (AIDS) is not permitted.

3.2.12 Any known positive test for Hepatitis B or Hepatitis C virus indicating acute or chronic infection is not permitted.

3.2.13 Patients who have received a live attenuated vaccine \leq 30 days prior to registration are not eligible.

4.0 TREATMENT PLAN

4.1 Overview

Nivolumab and ipilimumab combination will be administered intravenously until disease progression or intolerable toxicity. Nivolumab will be given at 240mg every 2 weeks for the first 16 weeks, and at 480mg every 4 weeks thereafter (starting with C2D29, 1 cycle = 12 weeks). Ipilimumab will be given at 1mg/Kg every 6 weeks over approximately 90 minutes. On days when both nivolumab and ipilimumab are administered, nivolumab should be given first, followed by ipilimumab about 30 minutes later. Scans will take place every 12 weeks for disease assessment. Note: Please refer to section 4.4 for patients who may continue treatment after initial progression.

4.2 Treatment Administration

Treatment Administration Summary						
Agent	Premedications	Dose	Route	Schedule	Cycle Length	Supportive Therapies
Nivolumab	None	240mg	IV infusion over ~30 minutes*	Q2Ws	12 weeks	As needed
		480mg	IV infusion over ~60 minutes	Q4W's		
Ipilimumab*	None	1mg/Kg	IV infusion over ~90 minutes*	Q6Ws		As needed

*On days when both drugs are administered, nivolumab should be given first, followed by ipilimumab ~30 minutes later.

